## **4. SELECTION OF SUBJECTS**

### **4.1 Study Population**

Patients will be recruited from the investigator's general patient population, and they must meet all of the inclusion/exclusion criteria listed below.

## 4.2 Inclusion criteria

All patients from Cardiovascular Institute of the South who were treated for femoropopliteal de novo/restenotic lesions or in-stent restenosis using Turbo Power laser atherectomy plus drug coated balloon angioplasty during 2016-2017.

## 4.3 Exclusion criteria

Patients will be excluded if there is any incomplete data on procedural approach and treatment.

### *Discontinuation of Subject Enrollment*

Whenever possible, every subject should remain in the study until the completion of all data collection is complete. However, a subject's participation may be discontinued at any time during the study. The rationale for discontinuation must be documented in the source documentation and in the data collection form.

Factors leading to discontinuation may include:

- Subject Withdrawal- A subject that has been consented prior to this amendment, may withdraw consent at any time for any reason or no reason at all. Withdrawal should not affect the subject's relationship with the physician, and no penalty or loss of benefits (if any) should occur. Every effort should be made by the research study staff to obtain the reason for the withdrawal of consent.
- Investigator Termination- An investigator may discontinue a subject in a study due to a significant adverse event or due to failure to cooperate with study requirements.
- Lost-To-Follow-Up- Lost to follow-up is defined as the inability to obtain a response from the subject on three separate days. These contacts may be telephone calls or emails to subject (or subject representative and/or primary care provider if subject unable to be contacted); however at least one effort should be a certified letter to the subject's last known address.

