**INVESTIGATOR: [name]**

**FUNDING: Investigator-Initiated Study Grant from Spectranetics**

### Protocol Summary:

Title:	Turbo Power Laser Atherectomy Combined with Drug Coated Balloon Angioplasty for the Treatment of Femoropopliteal De Novo/ Restenotic and In-Stent Restenosis Lesions
Study Objectives:	To determine outcomes of combined Turbo Power laser atherectomy + drug coated balloon (DCB) angioplasty for the treatment of femoropopliteal de novo/restenotic lesions and in-stent restenosis (ISR). Better understanding of these outcomes will help guide optimal treatment algorithms for this difficult to treat cohort of patients.
Primary Endpoint:	Rate of freedom from target lesion revascularization (TLR) at one year
Secondary Endpoints:	
 
• Procedural success (<math>\leq 30\%</math> residual stenosis)
 
• Procedural safety (freedom from significant embolization (sequelae), or dissection)
 
• Freedom from major amputation at 30d, 6mo & 12mo
 
• Freedom from death at 30d, 6mo & 12mo
 
• Freedom from TLR 6 months
 
• Patency at 12 months (up to 20 patients)
 

Study Population:	The intended population will consist of all patients undergoing endovascular treatment of femoropopliteal de novo/restenotic lesions and in-stent restenosis with Turbo Power + DCB treatment.
Design:	This is a retrospective, single-site, non-randomized study.
Sample Size:	Up to 120 patients will be enrolled at Cardiovascular Institute of the South
Treatment	De novo, restenotic or in-stent restenosis lesions treated with Turbo Power Laser atherectomy + Drug-coated balloon angioplasty
Inclusion criteria:	All patients from Cardiovascular Institute of the South who were treated for femoropopliteal de novo/restenotic lesions or in-stent restenosis using Turbo Power laser atherectomy plus drug coated balloon angioplasty between 2016-2017.
Exclusion criteria:	Any incomplete data on procedural approach and treatment.
Duration:	Review of patient data and inclusion into the study is expected to take up to 6 months. Patient data will be included through 12 months post-procedure.
Study start:	Upon receipt of all appropriate approvals and a fully executed contract with the site prior to that site enrolling.

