## **3. DESIGN**

This is a retrospective, single-site, non-randomized study. Up to 120 subjects will be included in this study at Cardiovascular Institute of the South. Patient data will be reviewed through 12 months post-procedure. Out of the 120 patients, up to 20 patients will be included for a sub-analysis of patency. These 20 patients must be compliant with physician discharge instructions to be included in this cohort.

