## 4.4 Treatment Group

Treatment was performed at the physician's discretion. The subjects included in this retrospective study were treated with Turbo Power laser atherectomy as well as drug-coated balloon angioplasty.

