## 5. SAMPLE SIZE AND STATISTICAL CONSIDERATIONS

**5.1** The study is designed to include up to 120 patients. Descriptive statistics (arithmetic mean, median as indicated, minimum and maximum and standard deviation) will be calculated for continuous variables. Absolute frequencies and percentages will be obtained for qualitative variables. 95% Confidence intervals will be provided. In

calculation of percentages, patients with missing data will not be considered, unless otherwise specified. All baseline characteristics will be summarized. Descriptive statistics will be used to summarize the values and changes from baseline across time.

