## **6. PROCEDURES**

### **6.1 Data Review**

All patients from Cardiovascular Institute of the South who were treated for femoropopliteal de novo/restenotic lesions or in-stent restenosis using Turbo Power laser atherectomy plus drug coated balloon angioplasty between 2016-2017 will be considered for study enrollment.

A review of the study candidate's medical history, procedure and data 12-months post-procedure will be performed and documented on the study CRFs.

Up to 20 patients that have been compliant with the physician's discharge instructions will be included in a subgroup. This subgroup will be specifically reviewed for long-term patency by the duplex ultrasound core lab. These patients will have a duplex ultrasound conducted within 305-425 days post-procedure ( $\pm 60$  days of 12-months post-procedure).

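### The Investigator Termination clause leaves room to stop chart abstraction for an outcome-related reason; the likely effect is small, and a short text edit closes the gap

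*Combined protocol and SAP*

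**What the plan says.** The unnumbered section Discontinuation of Subject Enrollment (after Section 4.3) starts from a default that subjects stay in, where possible, until data collection is finished. It then allows discontinuation at any time and lists three grounds. The one at issue reads: "An investigator may discontinue a subject in a study due to a significant adverse event or due to failure to cooperate with study requirements". For every discontinuation, "The rationale for discontinuation must be documented in the source documentation and in the data collection form". Section 9 defines no adverse-event term. The neighbouring withdrawal bullet refers to an earlier consented phase: "A subject that has been consented prior to this amendment, may withdraw consent at any time".

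On treatment, Section 4.4 says: "The subjects included in this retrospective study were treated with Turbo Power laser atherectomy as well as drug-coated balloon angioplasty". Section 7.2 requests a consent waiver on the ground that the data are already in existence.

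On follow-up, the Protocol Summary says "Patient data will be included through 12 months post-procedure" and Section 3 says "Patient data will be reviewed through 12 months post-procedure". Section 6.1 says that a review of medical history, "procedure and data 12-months post-procedure will be performed and documented on the study CRFs". None of the three mentions discontinued subjects.

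On missing data, Section 5.1 rules that in "calculation of percentages, patients with missing data will not be considered, unless otherwise specified". Section 8.2 commits to pursuing missing values and, where that fails, to sensitivity analyses under scenarios it does not specify. Section 8.5 asks that each CRF item be completed or its absence explained. Section 8.3 has a rule for data after a subject leaves, but only when authorization is revoked: earlier data may be used, and permission to record vital status is sought.

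**The concern.** In a prospective treatment trial, an investigator may need to take a subject off the study. Here there is no study treatment left to stop. For TLR, major amputation and death, which are read from the chart, ending participation can only mean ending abstraction. The section itself sets being discontinued against remaining until data collection is complete.

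The trigger can be related to outcome, and the person deciding may have the record in view. Suppose a patient is terminated after an adverse event, and later TLR, amputation or death status is not abstracted. Section 5.1 would then take that patient out of the relevant percentage. The study's product is a set of single-arm descriptive percentages with confidence intervals, and an interval on the remaining patients would not reflect such a loss. The outcomes concerned would be in charts already due for review, so the loss is avoidable.

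**Working it through.** **Reading the sections together**

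1. Does any section say abstraction continues after investigator termination? No. The Protocol Summary, Section 3 and Section 6.1 give a general 12-month rule, and the discontinuation section gives a specific way out of the study. Nothing reconciles the two.
2. Does another section close the gap? Only in part. Section 8.2 does not say whether missing values are pursued after discontinuation. Under Section 8.5, termination could itself serve as the explanation for a blank item. Section 8.3 covers revoked authorization only.
3. Which events are exposed? The reason for termination must be recorded, so an endpoint event that triggers termination is known and should count. Only later endpoints are exposed, such as 12-month amputation and death status after termination for a TLR, or a TLR that follows some other adverse event.

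**Size (illustration)**

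The plan gives a cap of 120 patients but no expected TLR rate and no expected number of terminations, so there is no figure of its own to reproduce. The values of E, r and k below are assumptions.

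Let N = 120, E = true events, r = patients dropped, and k = unabstracted events among them.

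- Observed freedom from event = 1 − (E − k)/(N − r)
- Shift from the true rate = (k − r·E/N)/(N − r)

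| True rate | r | k | Observed freedom from event |
|---|---|---|---|
| TLR 80.0% (E = 24) | 3 | 0 to 1 | 93/117 = 79.5% to 94/117 = 80.3% |
| TLR 80.0% (E = 24) | 6 | 0 to 3 | 90/114 = 78.9% to 93/114 = 81.6% |
| TLR 80.0% (E = 24) | 12 | 0 to 6 | 84/108 = 77.8% to 90/108 = 83.3% |
| TLR 70.0% (E = 36) | 6 | 0 to 3 | 78/114 = 68.4% to 81/114 = 71.1% |
| TLR 90.0% (E = 12) | 6 | 0 to 3 | 102/114 = 89.5% to 105/114 = 92.1% |
| Amputation 95.0% (E = 6) | 3 | 0 to 1 | 111/117 = 94.9% to 112/117 = 95.7% |

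Direction: at E = 24 and r = 6, r·E/N = 1.2. With k = 0 or 1 the rate is biased down, and with k = 2 or 3 it is biased up.

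Comparison with sampling error: the 95% half-width at 80% is 1.96·√(0.8 × 0.2/120) = 0.0716, or 7.2 points. The smallest r giving an upward shift of that size at E = 24 is:

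- r = 24 if half of those dropped have a TLR: 84/96 = 87.5%, a shift of 7.5 points
- r = 10 if all of them do: 96/110 = 87.3%, a shift of 7.3 points

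If all of 6 dropped patients had a TLR, the result is 96/114 = 84.2%, a shift of 4.2 points.

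**The case against.** The strongest reply is that the bullet looks like leftover wording from a consented design and may never be used. For harm to occur, someone must invoke it, stop abstracting a chart that already exists, do so before a later endpoint in that chart, and do so in enough patients to matter. The default is to keep subjects in, the 12-month review is stated without exception, the missing-data rule yields where something else is specified, and sensitivity analyses are promised. Section 8.1 already requires records of discontinuation. All of this stands, and it makes the point minor. It does not settle what happens to the chart of a terminated patient, and the sensitivity scenarios are unspecified.

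A reader might infer three stronger things that the documents do not support:

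- That a TLR leading to termination disappears from the primary endpoint. The required rationale keeps that event on record.
- That the plan orders abstraction to stop, or means to remove patients with poor outcomes. It is silent on the first and shows no intended use of the clause.
- That the clause acts on abstraction alone throughout the study. Sections 6.1 and 6.3 provide for a duplex scan in up to 20 patients, and the clause could act on that scan too.

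**Conclusion.** The gap is real and the point is minor. The clause permits an exclusion that may be related to outcome, in a study with no treatment to discontinue, and the other provisions reduce that risk without removing it. Freedom-from-event rates would be too high if the lost patients have more events than the rest, and too low if they have fewer. The documents settle neither direction nor size, so it should not be said that the reported rates will be inflated.

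On the assumptions shown (3 to 12 of 120 lost, at most half with an unabstracted TLR, true rate 80%), the shift lies between 2.2 points down and 3.3 points up, well inside the 7.2-point half-width. A shift as large as the half-width needs extreme assumptions. The reason to act is that the loss can be prevented at almost no cost.

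**What to change.** 1. Delete the Investigator Termination bullet for the chart-based endpoints, or limit it to the duplex scan in the patency subgroup.
2. State that an adverse event, non-cooperation or failure to reach the subject by contact does not end abstraction of existing records. Abstraction continues to 12 months or death, all included patients stay in the analysis set, and any event found is counted. This wording also keeps the new rule consistent with the adjacent Lost-To-Follow-Up bullet.
3. Where the chart itself holds no information to 12 months, treat the patient as missing and cover this in the Section 8.2 sensitivity analyses.
4. Make withdrawal of consent or revoked authorization the exception, handled as in Section 8.3: earlier data kept, permission for vital status sought.
5. Leave the compliance criterion for entry to the patency subgroup (Sections 3 and 6.1) unchanged.
6. Report discontinuations by reason. The reasons are already to be recorded, so only the reporting is new.

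The cost is a short text edit and full 12-month abstraction of the few charts that would otherwise have been closed early. No new patient contact is needed.

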### **7.2 Patient informed consent**

We are requesting a waiver of consent from IRB as this is a retrospective review and the data already exists. The patient's personal identifying information will not be compromised or disclosed.

Data from patients that have previously declined consent will not be included in the study.

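### Loss to follow-up is defined by unanswered contact attempts, although TLR, death and amputation come from record review, so no rule ensures that a record ending before 12 months is recognised

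*Combined protocol and SAP*

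**What the plan says.** The subsection Discontinuation of Subject Enrollment, after section 4.3, holds the only definition: "Lost to follow-up is defined as the inability to obtain a response from the subject on three separate days". The attempts may be by telephone or email. They may go to a representative or primary care provider if the subject cannot be reached, and "at least one effort should be a certified letter to the subject's last known address". Loss appears in a list introduced by "Factors leading to discontinuation may include". The same subsection opens with a counterweight: "Whenever possible, every subject should remain in the study until the completion of all data collection is complete".

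The rest of the plan describes a record review. Section 3 states "This is a retrospective, single-site, non-randomized study", with data reviewed through 12 months. Section 6.1 says that a review of history, procedure and "data 12-months post-procedure will be performed and documented on the study CRFs". Section 7.2 requests a consent waiver because "this is a retrospective review and the data already exists". No other source is named for TLR, death or amputation. Patency in up to 20 patients is different: it comes from a core-lab duplex at day 305-425.

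Three further provisions bear on the point. Section 5.1 leaves patients with missing data out of percentages unless otherwise specified. Section 8.2 has missing values queried and, if unresolved, examined in sensitivity analyses that it does not specify. Section 8.5 requires a missing CRF item to be explained.

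**The concern.** In a record review, a patient is followed for as long as the record shows contact with care. The plan's definition measures something else: whether someone replies during the review. The two can disagree in either direction.

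- A patient whose chart documents TLR, limb and vital status at 12 months, but who does not reply, meets the definition and may be discontinued. The plan does not say that the chart data then stay in the analysis.
- A patient whose last entry is at month 3, and whom nobody tries to contact, does not meet it. No TLR is recorded, so the patient can be scored TLR-free for the full year.

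The second case matters more. It inflates the primary endpoint, and can do the same for 12-month freedom from amputation and death, in a single-arm study where the estimate itself is the result.

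**Working it through.** **Text check.** No section defines follow-up by a last documented contact, sets a minimum observation for scoring a patient TLR-free, or gives a censoring rule. The exclusion criterion in section 4.3 concerns only procedural and treatment data, so short follow-up does not keep a patient out. Sections 5.1, 8.2 and 8.5 act on values recognised as missing. The absence of a TLR entry need not look like a missing value; it can look like no event.

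**Inputs.** From the plan: up to 120 patients and a one-year endpoint. The plan gives no TLR, loss or non-response rate, so there is no figure to reproduce. Assumed: one-year TLR 15% (18 events), half by month 6 (9 events); 12 or 36 event-free patients (10% or 30%) leave care at month 6 unflagged, with the same later risk as those who stay.

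**Events missed.** Risk after month 6 among those event-free at month 6: 0.075/0.925 = 8.1%. Missed TLRs: 12 × 0.081 = 1.0; 36 × 0.081 = 2.9. Observed TLRs: 18 − 1.0 = 17.0; 18 − 2.9 = 15.1.

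**Three ways to score the leavers (true freedom 85%).**

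| Rule | 12 leavers | 36 leavers |
|---|---|---|
| Counted as TLR-free | 1 − 17.0/120 = 85.8% (0.8 high) | 1 − 15.1/120 = 87.4% (2.4 high) |
| Dropped from the denominator | 1 − 17.0/108 = 84.2% (0.8 low) | 1 − 15.1/84 = 82.0% (3.0 low) |
| Censored at last contact | 0.925 × (1 − 8.0/99) = 85.0% | 0.925 × (1 − 6.1/75) = 85.0% |

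In the last row, the number at risk after month 6 is 120 − 9 − 12 = 99 or 120 − 9 − 36 = 75, and the later events seen are 9 − 1.0 = 8.0 or 9 − 2.9 = 6.1. Dropping leavers is biased because their event-free time is discarded while early TLRs are kept.

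**Range.** If records instead stop soon after discharge, nearly the full 15% is missed: 12 × 0.15/120 = 1.5 points to 36 × 0.15/120 = 4.5 points. With 25% TLR and the original month-6 pattern, later risk is 0.125/0.875 = 14.3%, and the overstatement is 12 × 0.143/120 = 1.4 to 36 × 0.143/120 = 4.3 points.

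**Non-responders with known status.** This applies only if their chart data were left out. Removing 12 of 120 patients who contain 0, 2 or 6 of the 18 TLRs gives 1 − 18/108 = 83.3%, 1 − 16/108 = 85.2% or 1 − 12/108 = 88.9%. The estimate barely moves unless non-response is related to TLR.

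**Precision.** The 95% half-width with complete follow-up is 1.96 × √(0.85 × 0.15/120) = 6.4 points. By Greenwood's formula with 36 censored it is 1.96 × 0.85 × √(9/(120 × 111) + 6.1/(75 × 68.9)) = 7.2 points. With 12 censored, 1.96 × 0.85 × √(9/(120 × 111) + 8.0/(99 × 91.0)) = 6.6 points.

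**The case against.** The strongest reply is that the definition has no stated role in the analysis. Section 5.1 excludes patients with missing data, not patients labelled lost, and no section links the two. That is correct. A reader might infer that lost status decides who is missing for the primary endpoint, but the documents do not say so. The overstatement arises because there is no chart-based rule for the end of follow-up, and rewording the definition alone would not cure it.

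Other stronger readings also fail:

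- *Early leavers are never flagged.* Sections 8.2 and 8.5 require missing items to be queried or explained, and a query could lead to contact and then to the label. What stands is that nothing guarantees this when a silent chart looks complete.
- *Non-responders are removed and their outcomes discarded.* Discontinuation is permitted, not automatic, and the plan prefers to keep subjects. No text deletes collected data, and section 8.3 lets earlier data be used even after authorization is revoked.
- *Patients may not be contacted.* Section 7.2 requests a waiver of consent; it does not bar contact. Some subjects were consented before the amendment, and up to 20 are to have a duplex, so a contact procedure can still serve a purpose. A primary care provider might also supply status.

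It is also fair that every rate above is assumed, and that the study is descriptive, with no hypothesis test or performance goal to be missed.

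**Conclusion.** The mismatch is real: the only stated definition of loss does not track whether 12 months were observed in the record, and no other rule does. The consequence is a possible bias, not a demonstrated one. On the main assumptions, freedom from TLR is overstated by about 0.8 to 2.4 points if all leavers go unflagged. That is smaller than the 6.4-point half-width of the confidence interval, but it runs in the favourable direction and the interval does not reflect it. The size depends on the assumed TLR rate, its timing, the share leaving care, and leavers having the same later risk as others. Possible discontinuation of patients with known status is the lesser problem, and matters only if their data were left out.

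**What to change.** 1. Define end of follow-up as the date of the last documented clinical contact in the record, or of death, and add that date to the CRF.
2. State that all available chart data are kept whatever the response to contact, and delete non-response as a ground for discontinuing chart-reviewed patients.
3. Estimate 6- and 12-month freedom from TLR, major amputation and death by Kaplan-Meier with 95% confidence intervals, censoring event-free patients at the date in item 1.
4. Report the number of patients with documented 12-month status.
5. State that early event-free leavers are not simply dropped from the denominator under section 5.1.

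Items 1 and 3 belong together: a last-contact date used only to exclude patients would exchange an upward bias for a downward one of similar size. Kaplan-Meier itself assumes that leaving care is unrelated to TLR risk, so item 4 is needed to let readers judge how much rests on that.

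The cost is a revised definition, one CRF date and a short analysis paragraph. More patients will be shown as incompletely followed, and intervals will be slightly wider: 6.6 to 7.2 points of half-width against 6.4 in the illustration.
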